#### **4.3.5. Replacement policy**

Patients who are prematurely discontinued from the study will not be replaced.

### **5. INVESTIGATIONAL PRODUCT(S)**

Patients who are eligible to participate in the study will receive Ferinject® and normal saline (placebo).

#### **5.1. Ferinject®**

Ferinject® is currently licensed up to doses of 1000 mg as an intravenous infusion for the treatment of iron deficiency when oral preparations cannot be used or are ineffective.

##### **5.1.1. Composition, packaging and storage**

A dark brown, non-transparent, aqueous solution. Ferinject® is available as 50 mg iron/mL solution for injection/infusion.

Ferinject® will be supplied by Vifor Pharma, Glattbrugg, Switzerland as 2ml and 10 ml solutions in a vial (type I glass) with bromobutyl rubber stopper and aluminium cap. One mL of solution contains 50 mg of iron as ferric carboxymaltose.

The study drug should not be stored above 30°C; it should not be refrigerated or frozen.

## **5.2. IMP preparation and administration**

### **5.2.1. IMP Preparation**

The total dose of Ferinject® to be administered will be 1000mg or 15mg/kg, whichever is the smaller.

The study treatments will be prepared either by the hospital pharmacy or as per local SOP at individual site.

Ferinject® will be diluted up to 50ml in sterile 0.9% sodium chloride solution.

The same volume of saline will be given as for the active drug.

### **5.2.2. IMP Administration**

Ferinject® will be administered by intravenous infusion and infused over 15 minutes. The patient will receive a single infusion of Ferinject® at either Week 0 or Week 12, depending on the treatment allocation.

## **5.3. Labelling**

The study drug will be labelled in accordance with local regulatory requirements.

## **5.4. Study drug accountability**

Accountability for the study drug at the study site is the responsibility of the Principal Investigator. The investigator will ensure that the study drug is used only in accordance with this protocol. Where allowed, the investigator may choose to assign some of the drug accountability tasks to a pharmacist or other appropriate individual.

Drug accountability records indicating the drug's delivery date to the site, inventory at the site, use by each subject, and end-of-study destruction and disposal of the drug, will be maintained by each clinical site. These records will adequately document that the subjects were provided the doses as specified in the protocol and should reconcile all study drug received from Vifor Pharma, Switzerland.

## **5.5. Treatment assignment and blinding**

### **5.5.1. Treatment assignment**

Patients will be randomised on 1:1 ratio to each treatment arm. Randomisation will be performed at the Baseline (Week 0) visit using InForm™. Randomisation will be stratified by gender, with an appropriate fixed block size, in order to ensure equal allocation to Ferinject® and placebo. The computer-generated randomisation list will be prepared by a statistician independent of the study team and will be provided to Imperial College staff (who are not otherwise involved in the study) responsible for building the InForm™ system.

### **5.5.2. Blinding**

This study will be conducted as a double-blind trial therefore the investigator, study staff, and patients will remain blinded to the patient's study treatment until the end of the study.

Ferinject® is a dark-brown solution. To ensure that the patient remains blinded to the treatment they are receiving, patients will be blindfolded for a short time during the infusion. Further details are described in the SPM.

Site personnel involved in the preparation and administration of the study drug will not be permitted to undertake any of the study assessments. In addition, an unblinded physician will be identified at each participating site and will be assigned to review iron profile results after patients have been dosed in order to prevent accidental unblinding of treatment allocation.

### **5.5.3. Emergency unblinding procedures**

The identity of the study treatment may be revealed only if the patient experiences a medical emergency whose management would be improved by the knowledge of the treatment assignment. Emergency unblinding can be performed immediately by the study investigator by examination of the remaining solution in the syringe or infusion line.

## **5.6. Concomitant medications**

### **5.6.1. Permitted concomitant medications**

Approved endothelin receptor antagonists (ERAs), phosphodiesterase-5 (PDE-5) type inhibitors and/or prostacyclin analogues are permitted for the treatment of PAH. The dose must be stable for at least 1 month prior to entry into the study.

### **5.6.2. Prohibited concomitant medications**

Patients are not permitted to take oral iron therapy whilst on the study.

## **6. VISIT AND ASSESSMENT SCHEDULE**

For a tabulated summary of all visits and assessments described in the following section see [Table 1](#).

It is recognised that the schedule of investigations may be difficult for patients with severe pulmonary hypertension. Therefore, it will be made clear to patients that they need not see through every investigation if they do not feel able to. Forgoing an investigation will not prevent patients from continuing the study.

### **6.1. Screening Visit**

The Screening Visit should be performed no more than 28 days prior to the Baseline/Randomisation Visit.

Participants' eligibility with respect to IPAH status and Iron status will usually be determined using from routine outpatient clinical record. The following data will be recorded during the visit or obtained from the hospital records where possible.

- Obtain written informed consent
- Demographics
- Medical history
- Physical examination
- Concomitant medications

- Vital signs: Resting supine blood pressure (BP), pulse measurement, temperature, pulse oximetry, height and weight.
- Modified NYHA/WHO Functional Class
- 6MWT and Borg dyspnoea index
- Blood samples for routine haematology, blood chemistry (including iron parameters, sTfR (where available) and serum pregnancy test where clinically indicated (woman of childbearing potential only).

Any missing or unavailable data (e.g. 6MWT or pregnancy test) or data which are not collected during routine outpatient visit should be collected at this visit or at Visit 1 after written informed consent has been obtained and before confirmation of the patient's eligibility for the trial. Randomisation will only occur after confirmation of eligibility. Screening and Baseline/randomisation procedures can be recorded in a combined visit.

### **6.2. Baseline/Randomisation Visit (Week 0)**

The patient will be admitted to the research unit for up to 3 days in order to undergo the following procedures:

- Physical examination
- Concomitant medications
- Document adverse events
- ECG
- Research blood sampling (NT pro-BNP, IL-6, hepcidin, sTfR and EPO). Neutrophil and peripheral blood mononuclear cell function and expression (Sheffield site only)
- Fasting glucose and insulin
- Incremental Cardiopulmonary Exercise Test
- Endurance Cardiopulmonary Exercise Test
- CAMPHOR questionnaire
- Cardiac MRI

Following completion of the above procedures, the patient will be randomised and receive an infusion of either the study drug (Ferinject®) or placebo (saline).

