--	---

	
16. Unable to perform a Cardiopulmonary Exercise Test i.e. due to syncope or musculoskeletal factors.
 
17. Patients who have received an investigational medicinal product within 30 days of entering the baseline visit

TREATMENT	
All the study participants will attend a screening visit, two treatment periods at Week 0 and Week 12, telephone visits at Week 2 and Week 14 and a follow up visit at Week 24 to evaluate the kinetics of iron re-depletion.
 
Potential participants will be screened using data collected during their routine outpatient appointment at the Pulmonary Hypertension Service. Any unavailable or missing data will be collected at the baseline visit (week 0) once the patient has provided written informed consent.
 
Eligible participants will be admitted to the research unit for up to 3 days in order to complete the Baseline (Week 0) assessments including a physical examination, medical history, ECG, bloods to assess routine haematology and clinical chemistry and measure biomarkers, 6-Minute Walk Test, CAMPHOR questionnaire and incremental and endurance cardiopulmonary exercise tests (CPET).
 
As outlined in Figures 1, following completion of the Baseline assessments at Week 0 patients will be randomly allocated 1:1 to receive an infusion of either Ferinject® or saline.
 
At Week 2, participants will attend a phone call from the research unit for a follow up visit. This will include any AE or medication and PGA questionnaire.
 
At Week 12 all participants will be admitted to the research unit for up to 3 days to repeat the assessments done at Baseline (Week 0). Following completion of the Week 12 procedures, the patients will be switched to the other treatment arm (i.e. those who received Ferinject® at baseline will be administered a saline infusion, and vice versa).
 
Thereafter participants will have a telephone follow up assessments at Weeks 14. The assessments at these visits are the same as for Week 2.
 
Participants will have a final hospital follow up visit at Week 24 during which the assessments will be the same as those performed at baseline and Week 12.
 
At selected centres participants will be given the option to undergo additional cardiac MRI (Weeks 0, 12 and 24).
 
At the Sheffield site only, if participants agree, they will have two extra blood samples taken (50 ml extra in total) to assess neutrophil and peripheral blood mononuclear cell function and expression at Week 0 and 2 or Week 0 and 12 of study participation.

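### For a woman tested at a separate screening visit, no line clearly requires a repeat pregnancy test before the first infusion, so the result relied on may be about 28 to 30 days old

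*Protocol*

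**What the plan says.** Section 4.3.2 excludes pregnant and lactating women (criterion 11).

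**Before the first infusion.** Section 6.1 lists, at screening, a "serum pregnancy test where clinically indicated (woman of childbearing potential only"). On timing it says: "The Screening Visit should be performed no more than 28 days prior to the Baseline/Randomisation Visit". Section 6.2 gives the Week 0 procedures without a pregnancy test and then states: "Following completion of the above procedures, the patient will be randomised and receive an infusion of either the study drug". The pregnancy row of Table 1 is marked at Screening, Week 12 and Week 24, and is blank at Week 0.

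**Before the second infusion.** Section 6.4 lists the serum test for women of childbearing potential, without the clinical-indication qualifier. Dosing follows the listed procedures in the same admission.

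**Provisions that fill gaps.** Section 6.1 has a catch-up clause. It opens "Any missing or unavailable data (e.g. 6MWT or pregnancy test") and directs that such items be collected at screening or Visit 1, after consent and before eligibility is confirmed. It adds "Randomisation will only occur after confirmation of eligibility" and "Screening and Baseline/randomisation procedures can be recorded in a combined visit". The Study Summary likewise says: "Any unavailable or missing data will be collected at the baseline visit (week 0) once the patient has provided written informed consent".

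**The concern.** The two infusions are blinded alternatives given 1:1, so about half of the participants receive their only iron dose at Week 0. One would expect the check of criterion 11 to be at least as well placed before that infusion as before the one at Week 12. On the page it is not. The first check is tied to a screening visit that may be four weeks earlier, and it carries a qualifier that the later check lacks.

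At stake is whether a woman who conceived after a negative screening test, or was too early for that test to detect, could be randomised and infused with no further check. The next test that is listed expressly comes at Week 12, after the first infusion. Agreed contraception (inclusion criterion 8) makes this unlikely, and pregnancy is a listed reason for withdrawal (section 4.3.4). Neither is a check made before the dose.

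**Working it through.** No sample size, power or alpha figure bears on this point, and the plan states no figure to reproduce. The check is a comparison of texts and one interval calculation.

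**Inputs.** Screening is at most 28 days before Week 0 (section 6.1, Table 1). The Week 0 and Week 12 admissions last up to 3 days (sections 6.2, 6.4). I count the 28 days to day 1 of the admission.

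**Longest interval from test to infusion.**

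- First infusion, test at a separate screening visit: 28 days to day 1, plus 3 − 1 = 2 days if the infusion falls on day 3, so 28 + 2 = 30 days.
- First infusion, missing test done at Visit 1, or visits combined: 0 to 2 days.
- Second infusion, test done in the Week 12 admission: 0 to 2 days.

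**Does any line require a repeat at Week 0 for the first of these groups?**

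| Text | What it supports |
|---|---|
| 6.2 procedure list | No pregnancy test listed |
| Table 1, pregnancy row | Blank at Week 0 |
| 6.1, catch-up clause | Covers a missing or unavailable test; a woman already tested is not missing one |
| 6.1 and Table 1 footnote, combined visit | Optional |
| 4.1 | Describes Week 12 as repeating Baseline and Week 24 as the same as Weeks 0 and 12; since 6.4 and 6.6 list the test, this points towards a Week 0 test |
| 7.8.1 with Table 1 | The pregnancy test is among the routine laboratory tests, and routine laboratory assessments are marked at Week 0; this also points towards a test |

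The last two rows suggest a Week 0 test without settling it. The wording in 4.1 cannot be wholly literal: section 7.10 places the Patient Global Assessment at Weeks 2, 12, 14 and 24 and not at Week 0, so the three visits are not identical. As for routine bloods, Table 1 gives pregnancy testing a row of its own, and that more specific row is blank at Week 0.

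**The case against.** The strongest reply is that the silence in 6.2 and Table 1 is weak evidence. The 6.2 list is incomplete: it omits vital signs and routine bloods, which Table 1 marks at Week 0. Blank cells are no better guide: the six-minute walk row is also blank at Week 0, although section 4.1 and the Study Summary name the walk test as a Baseline assessment. Section 6.1 pairs the walk test and the pregnancy test as examples of data to be completed before eligibility is confirmed. A blank therefore fits a test done at screening or at a combined visit. This stands, and it is why the text is called ambiguous and not plainly deficient.

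It can also be said that a negative serum test within about four weeks, with agreed contraception, is adequate, that the documents set no shorter validity period, and that a fresh test after 12 weeks is natural in itself. These arguments limit the weight of the point. They do not supply a line that requires a repeat before the first dose.

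Two stronger readings are tempting, and the documents do not support them.

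- A reader might infer that some women of childbearing potential are never tested before the first infusion because the test was judged not indicated. The parenthesis in 6.1 may simply define the indication, and the catch-up clause treats the test as expected data, so this group is probably empty. The wording only leaves the possibility open.
- A reader might infer from section 6 ("Forgoing an investigation will not prevent patients from continuing the study") that the test can be declined. That sentence concerns the burden of the schedule in severe disease and continuing in the study. Eligibility before randomisation is governed by 6.1.

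**Conclusion.** The point holds in a narrow form. For a woman tested at a separate screening visit, no line clearly requires a repeat before the first infusion. The result may be up to 28 days old at Week 0, or about 30 days if she is infused on day 3, against 0 to 2 days for a test done in the Week 12 admission. The qualifier in 6.1 adds avoidable doubt about whether the screening test is mandatory.

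The intervals assume that the sample is taken at the screening visit itself and that the 28 days run to day 1 of the admission. The Protocol gives neither the number of women of childbearing potential nor a conception rate, so the expected number of undetected pregnancies cannot be estimated and none is claimed. It also states no specific fetal hazard. This is a minor participant-safety and wording point, and the primary analysis is unaffected.

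**What to change.** - In section 6.1, replace the qualifier and its parenthesis by a plain requirement for all women of childbearing potential.
- Add a serum pregnancy test at Week 0 to section 6.2 and to the pregnancy row of Table 1, met by the screening test if the visits are combined.
- State that a negative result is required before randomisation.

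The cost is one extra 1.5 mL sample per woman of childbearing potential (the volume given in section 7.8.3) and a short wait for the result, which fits an admission of up to 3 days. A Week 0 test can still miss a very early pregnancy, so it narrows the gap without closing it.

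No restated blood total is proposed. Section 7.8.3 budgets 7 chemistry, 7 haematology, 6 research and 2 pregnancy collections, whereas Table 1 marks 4 visits for routine laboratory tests, 3 for research blood and 3 for pregnancy testing. Adding one sample to the printed total would carry those differences forward, so that table needs its own reconciliation.

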### **6.3. Week 2 (+/- 3 days) Telephone Follow up**

Patients will undergo a telephone review at week 2 to check for AEs and concomitant medication. The PGA questionnaire will be completed over the phone.

### **6.4. Week 12 (+/- 3 days)**

The patient will be admitted to the research unit for up to 3 days in order to undergo the following procedures:

- Physical examination
- Concomitant medications
- Document adverse events
- Vital signs: Resting supine blood pressure (BP), pulse measurement, temperature, pulse oximetry and weight
- ECG
- Modified NYHA/WHO Functional Class
- 6MWT and Borg dyspnoea index

- Blood samples for routine haematology, blood chemistry, (including iron indices), and serum pregnancy test (woman of childbearing potential only)
- Research blood sampling (NT pro-BNP, IL-6, hepcidin, sTfR and EPO; neutrophil and peripheral blood mononuclear cell function and expression (Sheffield site only)
- Fasting glucose and insulin (taken after an overnight stay and before dosing)
- Incremental Cardiopulmonary Exercise Test
- Endurance Cardiopulmonary Exercise Test
- Cardiac MRI (where the facility is available)
- CAMPHOR questionnaire
- Patient Global Assessment (PGA)

Following completion of the above procedures, the patient will be administered either the study drug (Ferinject®) or placebo (saline).

#### **6.5. Week 14 (+/- 3 days) Telephone Follow up**

Patients will undergo a telephone review as at week 2 to check for AEs and concomitant medication. The PGA questionnaire will be completed over the phone.

#### **6.6. Week 24 (+/- 3 days)**

The patient will attend the research unit in order to undergo the following procedures (these assessments can either be done as outpatient visits or on an inpatient basis involving an overnight stay at selected centres):

- Physical examination
- Concomitant medications
- Document adverse events
- Vital signs: Resting supine blood pressure (BP), pulse measurement, temperature, pulse oximetry and weight
- ECG
- Modified NYHA/WHO Functional Class
- 6MWT and Borg dyspnoea index
- Blood samples for routine haematology, blood chemistry, (including iron indices), and serum pregnancy test (woman of childbearing potential only)
- Research blood sampling (NT pro-BNP, IL-6, hepcidin, sTfR and EPO)
- Fasting glucose and insulin (taken after an overnight stay)
- Incremental Cardiopulmonary Exercise Test
- Endurance Cardiopulmonary Exercise Test
- Cardiac MRI (where the facility is available)
- CAMPHOR questionnaire
- Patient Global Assessment (PGA)

### **7. STUDY ASSESSMENTS**

#### **7.1. Physical Examination and Medical History**

Physical examinations will be performed to ensure suitability according to the inclusion and exclusion criteria at screening and to document the health status at the time points specified in the Schedule of Events (Table 1). The physical examination comprises measurement of height and body weight and a routine medical examination.

A medical history will be recorded at screening or at Visit 1. The medical history will elicit information concerning existing medical conditions, major illnesses, and related surgical procedures. Any prescribed or over-the-counter medications that the subject received within the past 30 days should be recorded on the CRF. Medication prescribed for the treatment of PAH for the 8 weeks prior to enrolment should be recorded on the CRF. Subjects will be instructed to notify the study doctor before beginning new prescribed or over-the-counter medications.

## **7.2. Modified NYHA (WHO) Classification**

Functional assessment of PAH will be made according to the modified New York Heart Association (NYHA) (WHO) classification system (World Symposium on Primary Pulmonary Hypertension, 1998, Evian, France, sponsored by the World Health Organization).

Class I:	Patients with PAH without limitation of physical activity. Ordinary physical activity does not cause increased dyspnoea or fatigue, chest pain, or near syncope.
Class II:	Patients with PAH resulting in slight limitation of physical activity. No discomfort at rest. Normal physical activity causes increased dyspnoea or fatigue, chest pain, or near syncope.
Class III:	Patients with PAH resulting in marked limitation of physical activity. There is no discomfort at rest. Less than ordinary activity causes increased dyspnoea or fatigue, chest pain, or near syncope.
Class IV:	Patients with PAH with inability to carry out any physical activity without discomfort. Indications of manifest right heart failure. Dyspnoea and/or fatigue may even be present at rest. Discomfort is increased by the least physical activity.

## **7.3. Vital signs**

Systolic and diastolic systemic BP will be measured by means of either a standard manual or an automatic BP measuring device (cuff method). For each subject, the same method should be used during the entire study, and the type of device used should be recorded on the CRF. The same arm will be used for each measurement of BP, and BP will be measured after 5 minutes seated.

At each visit heart rate (HR) and oxygen saturation will be measured by pulse oximetry after the subject has been at rest for at least 5 minutes.

## **7.4. Endurance cardiopulmonary exercise test**

Endurance exercise testing has been shown to be a much more sensitive indicator of change in exercise capacity in studies of rehabilitation in chronic lung disease, but remains an exploratory endpoint in pulmonary hypertension. Work rate will be set at 80% of the patient's peak work rate achieved on the baseline CPET and patients will be asked to exercise to a point where they are unable to continue. The same equipment and monitoring will be used as in the incremental test and end-test  $VO_2$  will be used to gauge validity of the test, as it ought to be the same as the patient's maximal  $VO_2$ . Measurement of steady-state gas exchange will be made also at 3 minutes and peak. Details are described in the SPM.

## **7.5. Six minute walk distance**

Distance walked during an unencouraged 6 minute walk test conducted according to American Thoracic Society (ATS) guidelines (8). This is a standard tool for the study of functional capacity in PAH patients and is primarily determined by cardiac output and hence right ventricular function. We are aware that a possible increase in haemoglobin might be a confounding factor, improving 6 minute walk not because of the increase in cardiac output but because of increased oxygen delivery.

This is the rationale behind assessing exercise haemodynamics. We will interpret the 6 minute walk in the context of the overall results. [The screening walk test may be done according to local protocol.]

